STUDY PROTOCOL

Project title: Addressing Insufficient Positive Airway Pressure Use Among Older Veterans With Obstructive Sleep Apnea (IIR 20-046)

PI: [name]

SPECIFIC AIMS

Primary Aim 1: Test the efficacy of a novel program for improving PAP usage, compared to a general sleep education attention control program, among middle-aged and older Veterans with previously diagnosed OSA who have insufficient PAP use.

- Hypothesis 1a: Compared to control, Veterans who receive the intervention will have greater objectively measured PAP use (mean hours of PAP use per night) at 6-months follow-up.
- Hypothesis 1b: Effects will be sustained at 12-months follow-up.

Secondary Aim 2: Test the efficacy of this novel program for improving sleep quality, daytime sleepiness and sleep-related function compared to the control program.

- Hypothesis 2a: Compared to control, Veterans who receive the intervention will report better sleep quality (PSQI), less daytime sleepiness (ESS), and better sleep-related function (FOSQ-10) at 6-months follow-up.
- Hypothesis 2b: Effects will be sustained at 12-months follow-up.

Exploratory Aim 3: Test the efficacy of this novel program for improving health-related quality of life compared to the control program.

- Hypothesis 3a: Compared to control, Veterans who receive the intervention will report better health-related quality of life (PROMIS-29 v2.1 Physical and Mental Health Summary Scores) at 6-months follow-up.
- Hypothesis 3b: Effects will be sustained at 12-months follow-up.

RESEARCH DESIGN AND METHODS

Basic Study Design

This is a 4-year, randomized controlled trial testing a novel intervention for older Veterans (aged ≥ 50 years) with previously diagnosed OSA, who were prescribed PAP therapy but have insufficient PAP use (defined as no use or use that does not meet Medicare standards). The intervention involves a structured, supervised approach (with weekly oversight by telephone with a study psychologist) that can be provided by individuals from various disciplines to maximize future implementation. The intervention is 6 months in duration, with sessions at weeks 1,2,3,4 and 8, and brief follow-up sessions at 12,16, 20, and 24 weeks. Core components of the intervention include:

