1) educational and behavioral approaches to improve both PAP use and poor sleep behaviors, 2) individualized self-management and troubleshooting techniques to address factors that contribute to the participant's insufficient PAP use, and 3) ongoing review of objective evidence of PAP use. The intervention will be compared to an active control condition that aligns with "optimal usual care" and controls for the added social attention in the intervention group. Structured outcome assessments will be collected at baseline, post-treatment (i.e., after completion of the 5th intervention or control session), and at 6- and 12-months. The primary outcome is objectively measured PAP use at 6 months, with testing for maintenance of effects at 12-month follow-up. Secondary measures include sleep quality, daytime sleepiness and sleep-related function; and an exploratory measure of health-related quality of life, at 6- and 12-months. All data will be collected by research personnel and analyses will be intention to treat.

We will also collect measures of the process of the intervention and explore participants' experiences and attitudes related to the intervention which may act as potential facilitators and barriers to future implementation. We will focus on four specific intervention implementation outcomes identified by Proctor et al, including acceptability and appropriateness of the intervention (from the participant point of view), fidelity and implementation cost of the intervention (estimated from staff time to provide the intervention).

Setting

The study site will be VA Greater Los Angeles Healthcare System (GLAHS), which has one of the most diverse Veteran populations in the US. During the ongoing COVID-19 pandemic, all study activities will be conducted virtually via telephone and video.

Study Protocol

Version: 10/20/2025

Sources used to obtain study sample

We will identify the initial study sample from VA administrative databases. We will also ask VAGLAHS providers to provide us with names of patients who meet basic study eligibility criteria. Veterans identified from any of these sources will be mailed a recruitment letter and opt-in/out form as described below.

VA Corporate Data Warehouse (CDW)

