1	1	45 minutes	General information about sleep, overview of sleep cycles, normal quantity and quality of sleep, consequences of sleep for health and well-being, importance of sleep for health benefits
2	2	30 minutes	Sleep across the lifespan, sleep stages, circadian rhythms, general health education
3	3	30 minutes	Sleep and health, sleep hygiene (sleep environment considerations)
4	4	30 minutes	Sleep hygiene (diet, exercise, caffeine), daytime relaxation techniques
8	5	30 minutes	Review of content from prior sessions, daytime stress reduction
12, 16, 20, 24	N/A	10 minutes	Brief, non-directed, check-in phone call

Sample Size

Our proposal estimated that we will need to consent (i.e., enroll) 225 individuals to reach the target sample of 90 randomized participants. While enrolled participants will meet basic eligibility criteria, informed consent is required to administer the questionnaires and conduct the medical record review necessary to determine eligibility for randomization. In addition, participants may drop out of the study during the baseline assessment phase or may choose not to proceed with the randomization phase.

During the study, we used data collected from the study to re-run power analysis to inform whether a larger target for total number of randomized participants should be considered. Since PAP usage is based on telemonitoring, we have usage for all participants (0% attrition). For other outcomes we assumed a worse-case scenario of 20% attrition. For the PSQI, ESS and PROMIS questionnaires, we used the published Minimal Clinically Important Difference (MCID) to inform the detectable difference for each questionnaire. For the FOSQ, we could not find an MCID and calculated the detectable difference in terms of Cohen's *d*. The new analysis found a sample size of 106 achieved at least 80% power for each outcome (see Table below). Based on this new (larger) randomized sample size estimate, we continued enrollment until we achieved a sample of 106 randomized participants.

Primary Outcomes	Detectable difference	Power (% Attrition)	Revised required sample size
PAP usage (nightly)	≥1.7 hours/night	0.999 (0%)	n=90
Pittsburgh Sleep Quality Index (PSQI)	≥ 2.5 points	0.803 (20%)	n=106
Epworth Sleepiness Scale (ESS)	≥ 2.9 points	0.906 (20%)	n=106
Functional Outcomes of Sleep Questionnaire (FOSQ)	≥ d =0.64	0.806 (20%)	n=106
Exploratory Outcomes			
PROMIS- Physical	≥ 4.6 points	0.935 (20%)	n=106

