PROMIS-Mental Health	≥ 4.6 points	0.963 (20%)	n=106

Data Analysis

Primary Aim 1

Objective PAP use was collected from adherence reports downloaded from the PAP manufacturer's cloud-based data management system (i.e., Care Orchestrator for Philips Respiration devices and Airview for Resmed devices). Beginning with the first night after randomization, each block of 30 nights was considered a "month" (e.g., nights 1 to 30 were month 1, nights 31 to 60 were month 2, etc.). Data extracted from the adherence reports included the average hours of PAP usage per night. These variables were extracted using a customized program written in "R" software to create a dataset containing monthly PAP use data for each randomized participant. Average nightly PAP usage for the first six-months (nights 1 to 180) was computed by averaging the PAP usage for months 1 to months 6. An independent groups *t*-test was used to compare the average PAP usage between the treatment and control groups.

Aims 2 and 3

Aim 2 focuses on improvements in sleep quality (measured by the Pittsburgh Sleep Quality Index (PSQI), and its three subscales – Sleep efficiency, Perceived sleep quality, and Daily disturbances), daytime sleepiness (measured by the Epworth Sleepiness Scale (ESS), and sleep related function (measured by the Functional Outcomes of Sleep Questionnaire-10 item (FOSQ-10). Exploratory Aim 3 focused on health-related quality of life (measured by the PROMIS29-Mental Health and PROMIS29-Physical Health subscales).

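### Does the power table's "Primary Outcomes" heading turn PSQI, ESS and FOSQ into primary outcomes alongside PAP use?

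*Combined protocol and SAP*

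**What the plan says.** Four parts of the document bear on the ranking of outcomes.

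- **Specific Aims.** Primary Aim 1 concerns PAP use. The questionnaires come under the next aim: "Secondary Aim 2: Test the efficacy of this novel program for improving sleep quality, daytime sleepiness and sleep-related function compared to the control program". PROMIS-29 belongs to Exploratory Aim 3.
- **Basic Study Design.** "The primary outcome is objectively measured PAP use at 6 months", with maintenance tested at 12 months. Then: "Secondary measures include sleep quality, daytime sleepiness and sleep-related function".
- **Data Analysis.** Under Primary Aim 1, one t-test "was used to compare the average PAP usage between the treatment and control groups". Under Aims 2 and 3: "Aim 2 focuses on improvements in sleep quality (measured by the Pittsburgh Sleep Quality Index (PSQI", followed by ESS and FOSQ-10, and "Exploratory Aim 3 focused on health-related quality of life".
- **Sample Size.** The power analysis was re-run during the study "to inform whether a larger target for total number of randomized participants should be considered". The result was 106, justified by at least 80% power for every outcome. In the table, the heading "Primary Outcomes" stands above PAP use, PSQI, ESS and FOSQ, and a separate exploratory heading stands above the PROMIS rows. The last column gives a required size of 90 for PAP use and 106 for every other row.

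**The concern.** The heading cannot be put down to text extraction or read as a generic column title. The same table has a second heading for exploratory outcomes, so its rows were sorted by rank, and three of them were given a rank that the rest of the document denies them.

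The place matters as well. This table justifies the final number randomized, and the target was raised partway through using the study's own data. A reader who trusted the heading would conclude that three primary outcomes were short of power at 90 and that the increase protected the primary analysis. Nothing in the prose corrects that reading, because it refers only to power for each outcome. Four primary outcomes would also call for a multiplicity rule, and there is none. What would be at stake is a questionnaire result reported as a primary finding.

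**Working it through.** **1. The sections side by side**

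| Outcome | Specific Aims | Basic Study Design | Data Analysis | Power table tier | Required n |
|---|---|---|---|---|---|
| PAP use | Primary Aim 1 | Primary | Primary Aim 1 | Primary | 90 |
| PSQI | Secondary Aim 2 | Secondary | Aim 2 | Primary | 106 |
| ESS | Secondary Aim 2 | Secondary | Aim 2 | Primary | 106 |
| FOSQ | Secondary Aim 2 | Secondary | Aim 2 | Primary | 106 |
| PROMIS (two scores) | Exploratory Aim 3 | Exploratory | Exploratory Aim 3 | Exploratory | 106 |

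Three sections agree on every row. The table departs from them on three rows and only in the tier heading. The Data Analysis section does not use the word secondary; there the ranking comes from the aim numbers.

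**2. Can the table's figures be reproduced?**

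Only the FOSQ row can be checked without a standard deviation: d = 0.64, 20% attrition, N = 106, stated power 0.806. Alpha, sidedness and allocation are not given. I assume a two-sided 0.05 t-test with equal arms. Retained: 106 × 0.8 = 84.8, about 42 per arm. The noncentrality is d × √(n/2) = 0.64 × √21 = 2.93, on 82 degrees of freedom.

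- 42 per arm: power 0.826.
- 40 per arm: power 0.807, almost the stated value.

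The row is reproduced to within 0.02, so the sponsor's inputs are close to these but not identical.

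**3. Did the primary outcome need the increase?**

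Stated power is 0.999 at n = 90 with no attrition. Solving the same test for d at 45 per arm gives d ≈ 1.08, hence an implied SD of 1.7/1.08 ≈ 1.6 hours. With that d, 80% power needs about 15 per arm. PAP use did not need more than 90, as its own row says.

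**4. Which rows could have needed it?**

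Solve d from each stated power at 42 per arm, then apply it at N = 90 with 20% attrition (90 × 0.8 / 2 = 36 per arm):

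| Outcome | Stated power at 106 | Implied d | Power at 90 |
|---|---|---|---|
| PSQI | 0.803 | 0.62 | 0.74 |
| ESS | 0.906 | 0.72 | 0.86 |
| PROMIS-Physical | 0.935 | 0.77 | 0.89 |
| PROMIS-Mental | 0.963 | 0.83 | 0.93 |

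PSQI needs 42 per arm for 80% power, and 84/0.8 = 105, close to 106. On these assumptions PSQI is enough to explain the new target.

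FOSQ is left out. The Sample Size text says no MCID was found and the detectable difference was calculated as Cohen's d, so 0.64 may be the result of the calculation and not an input. Holding it fixed while lowering N would then be circular: at 36 per arm the difference detectable with 80% power would simply be about 0.67.

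**5. What changes if the heading is corrected?**

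The table's n column, the total of 106, the t-test for PAP use and the mixed-model contrasts for the questionnaires all stay as they are.

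**The case for a change.** The strongest case for acting is that a document should not contradict itself on which outcomes are primary, least of all in the table that supports a sample size revised mid-study, when the cure is a few labels and one sentence. If the heading were obeyed and four outcomes each tested at 0.05, the chance of at least one false primary result would be 1 − 0.95⁴ = 0.19 if they were independent, against 0.05 for one.

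The first part stands: the heading is wrong. The error-rate argument does not carry over. It describes a testing plan that no section proposes; the analysis text gives PAP use its own primary comparison and handles the questionnaires under other aims. Nor is the reason for the increase hidden. The prose sends the reader to the table, whose last column separates PAP use at 90 from everything else at 106. A sentence saying so would repeat what is already visible.

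**Conclusion.** This is a clerical slip and no change to the plan follows. The heading misplaces three outcomes, while the aims, the design section and the analysis section agree that PAP use at 6 months is the only primary outcome. An analyst working from those sections would report the same primary result and the same secondary results whether or not the heading was corrected.

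That conclusion rests on the text alone. The calculations only add that the primary outcome had ample power at 90 and that PSQI by itself could account for 106. They assume a two-sided 0.05 t-test, equal arms and 20% attrition for questionnaires. The questionnaires are in fact analysed by mixed-model contrasts, so the powers at 90 are illustrative. If the document is reissued for another reason, the tier labels could be tidied then.

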Participants with stable psychiatric/medical conditions, and those using medications for sleep will not be excluded.

Randomization

Participants will be randomized following guidelines of the Consolidated Standards of Reporting Trials (CONSORT). Stratified randomization will be used based on (stratum 1) any PAP use over the prior 12 months, versus (stratum 2) no PAP use over the prior 12 months, since this may predict treatment response. Within each stratum, randomization sequences will be "blocked" using a block size of n=4. The statistician will generate the stratified randomization sequence prior to study onset and it will be transferred to a series of "security envelopes" by another staff member (independent from the study) and stored in a secure location. Once eligibility is determined, another staff person (independent from the study) will open the next envelope in sequence within the appropriate stratum (i.e., for random allocation concealment). Participants will be randomized to the active intervention (i.e., behavioral intervention to improve PAP use) or the general sleep education control condition.

Intervention and control groups

The structure of the intervention and control conditions is identical. Participants in both groups will attend 5 VVC sessions over the course of 8 weeks, plus monthly follow-up telephone contacts for 4 additional months. The content of the two conditions is different and is explained in the tables below. Between session 1 and session 2 of the intervention and control conditions, participants (in both groups) who do not currently have a PAP device, or do not have the current PAP model dispensed by the Sleep Medicine clinic, will receive a new PAP device, alongwith new masks and tubing. To avoid delays in receiving the PAP device from the Sleep Medicine clinic, [name] (Clinic Director) has agreed that one of the research staff ([name]) a certified respiratory technician, can dispense the new PAP machine to the research participant. [name] will set-up the PAP according to the pressure prescription provided by a Sleep Medicine provider and will connect the modem for remote monitoring by Sleep Clinic staff as part of usual care. [name] has also given permission for [name] and the interventionists to access the clinic data so summary PAP usage reports can be obtained.

Note: No recalled Philip Respironics PAP devices will be dispensed to study subjects.

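### Randomization is stratified by prior PAP use but the primary t-test ignores the stratum, so its interval is too wide if the stratum predicts PAP hours

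*Combined protocol and SAP*

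**What the plan says.** The Randomization section states: "Stratified randomization will be used based on (stratum 1) any PAP use over the prior 12 months, versus (stratum 2) no PAP use" over the same period. The reason given is "since this may predict treatment response", and allocation within each stratum is blocked, "using a block size of n=4".

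The primary outcome is mean nightly PAP use over nights 1 to 180 (Data Analysis, Primary Aim 1). The analysis is stated in one sentence: "An independent groups *t*-test was used to compare the average PAP usage between the treatment and control groups". No stratum term, stratified test or adjusted sensitivity analysis follows. The mixed models for Aims 2 and 3 contain only group, time and their interaction. The only covariates mentioned are medication variables to be explored, in the section on medical chart review.

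Under Sample Size, the PAP usage row gives a detectable difference of "≥1.7 hours/night" with power 0.999, 0% attrition and n=90. The same section says "we continued enrollment until we achieved a sample of 106 randomized participants".

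**The concern.** Stratified blocking makes the arms nearly identical in their mix of prior users and non-users. Differences between the strata therefore hardly contribute to chance variation in the treatment difference. The two-sample t-test does not know this: its pooled SD contains the between-stratum spread, so its standard error describes an unstratified trial.

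The stratum is past PAP use and the outcome is future PAP use, so a link is plausible. The investigators thought it likely enough to stratify on. If there is a link, the interval for the primary effect is too wide and the test runs below its nominal level. At stake is the precision of the main estimate, and some power if the true effect is smaller or the SD larger than planned. A false positive is not at stake.

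**Working it through.** **Inputs from the documents.** Two strata, blocks of 4, 106 randomized, difference 1.7 h, power 0.999 at n=90, 0% attrition.

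**Assumptions.** Equal allocation and a two-sided 5% level, neither of which is stated for the primary test. R² is the share of variance in mean nightly PAP hours explained by the stratum. The documents do not give it, so I use 0 to 30%.

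**1. The plan's own power figure.** No SD is given, so 0.999 cannot be checked directly. Solving the noncentral t for power 0.999 with 45 per arm gives a standardized difference of 1.077, so SD = 1.7 / 1.077 = 1.58 h. Allowing for rounding of the power (0.9985 to 0.9995), the range is 1.52 to 1.62 h. If the power refers to 53 per arm, the SD is 1.72 h.

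**2. Standard errors.** With N randomized equally and total SD σ, the t-test uses variance 4σ²/N. Under stratified blocking the true variance is about 4σ²(1−R²)/N. Hence:

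- Excess standard error = 1/√(1−R²) − 1.
- True level of a nominal 5% test = 2Φ(−1.96/√(1−R²)).
- 95% CI half-width, t-test = t(104) × 1.579 × 2/√106 = 1.983 × 1.579 × 0.1943 = 0.608 h.
- 95% CI half-width, adjusted = t(103) × 1.579 × √(1−R²) × 2/√106.
- Gap between prior users and non-users that the R² implies, equal strata = 2σ√R².

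| R² (assumed) | SE too large by | True level | Half-width, t-test | Half-width, adjusted | Implied gap |
|---|---|---|---|---|---|
| 0 | 0% | 5.0% | 0.608 h | 0.608 h | 0 h |
| 5% | 2.6% | 4.4% | 0.608 h | 0.593 h | 0.71 h |
| 10% | 5.4% | 3.9% | 0.608 h | 0.577 h | 1.00 h |
| 20% | 11.8% | 2.8% | 0.608 h | 0.544 h | 1.41 h |
| 30% | 19.5% | 1.9% | 0.608 h | 0.509 h | 1.73 h |

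An R² of 30% needs a gap between strata as large as the planned treatment effect, so 20 to 30% is the upper end. With a 30/70 split of strata the gaps are 0.77, 1.09, 1.54 and 1.89 h for R² of 5 to 30%.

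**3. Simulation** (N=106, blocks of 4 in two equal strata, no treatment effect, 10,000 runs per case):

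| R² | Type I error, t-test | Type I error, adjusted |
|---|---|---|
| 0 | 0.049 | 0.049 |
| 5% | 0.042 | 0.047 |
| 10% | 0.038 | 0.048 |
| 20% | 0.030 | 0.052 |
| 30% | 0.019 | 0.049 |

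A 30/70 split gave the same pattern: 0.048 falling to 0.020 for the t-test, and 0.048 to 0.053 for the adjusted model.

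**4. Power.** At 1.7 h and the implied SD, simulated power was at least 0.999 for both analyses in every case. If the SD were 2.0, 2.5 or 3.0 h, t-test power at 53 per arm would be 0.991, 0.934 or 0.824. For an effect with about 80% nominal power, simulation gave the following, t-test then adjusted: 0.80 and 0.81 (R² 5%), 0.82 and 0.84 (10%), 0.82 and 0.88 (20%), 0.84 and 0.92 (30%).

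**The case against.** **The consequence is small.** This stands. The half-width shrinks by about 1, 2, 4 or 6 minutes a night at R² of 5, 10, 20 or 30%, against a planned difference of 102 minutes. The error is conservative, so a positive result is not undermined.

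**R² is unknown and may be near zero.** This also stands. All participants were selected for insufficient use, so those in the prior-use stratum are low users too. Participants in both arms who "do not currently have a PAP device, or do not have the current PAP model dispensed by the Sleep Medicine clinic" receive a new device. Both facts could narrow the gap between strata. The concern is conditional for that reason.

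**The stated rationale may mean effect modification.** Read literally, a predictor of treatment response need not predict hours when treatment does nothing, and the t-test would then have its nominal level under the null. The additive model is not exact in that case either. Take a 1.0 h stratum gap in the treated arm only, equal strata of fixed size, residual SD 1.5 h and 53 per arm:

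- True SE = √(2.25 × 2/53) = 0.291.
- t-test SE = √((2.50 + 2.25)/53) = 0.299.
- Additive-model SE = √(2.3125 × 2/53) = 0.295.

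The adjusted model removes about half of the excess. It is still the closer of the two.

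**No CI or significance level is stated for Aim 1.** Correct: the 95% interval is named only for Aims 2 and 3. The 5% level here is my assumption. The percentage excess in the standard error depends on neither that level nor the back-solved SD.

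**The text is in the past tense, so a change now could be post hoc.** This is a fair caution. It is met by disclosure and by reporting both analyses.

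**Conclusion.** The concern holds. The primary analysis does not reflect the stratified randomization, and to the extent that prior PAP use predicts PAP hours, the t-test gives too wide an interval and a level below nominal. The excess in the standard error runs from 0% (R² of 0) to 19.5% (R² of 30%), and is 2.6 to 5.4% for R² of 5 to 10%. This rests on assumed R² values, equal allocation, a two-sided 5% level and a stratum that acts on PAP hours themselves. The half-widths in hours also rest on the SD of 1.58 h implied by the power table.

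This is a change that should be made because it is nearly free. It does not threaten the validity of a positive finding.

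**What to change.** Analyse mean nightly PAP use over nights 1 to 180 with a linear model containing treatment and randomization stratum. Report the adjusted difference with its 95% CI, and report the unadjusted t-test alongside. If outcome data had been seen before this model was specified, say so in one sentence.

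Add baseline PAP hours only if an averaging window before randomization can be defined and is available for everyone (0 for the stratum with no use). The section on intervention and control groups notes that some participants have no device or not the current model, so this may not be possible.

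The cost is one degree of freedom and a re-run of one model. The stratum is already recorded for every randomized participant, since it determined which envelope was opened.

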We will use VA administrative data to identify a sample of Veterans who meet basic eligibility criteria. Authorized VA project team member(s) will work with VINCI programmers to pull a sample from CDW. Study inclusionary criteria will be applied to select eligible Veterans for recruitment. The sample file will include Veterans aged 50 years and older who have a diagnosis of obstructive sleep apnea and have received care from a VAGLAHS facility. To help capture eligible patients with fresh contact information, this process will be repeated 2-3 time during the study recruitment period. Specific data requested from CDW will include:

- Unique patient identifiers (e.g., SSN, patient ICN, Patient SID, etc.)
- Contact information (e.g., name, residential address, zip code, telephone numbers, etc.)
- Demographic and Veteran characteristics (e.g., dob, gender, race/ethnicity, dod, Veteran status, income, etc.) Treatment and Diagnoses (e.g., clinic stop codes, station codes, encounter dates, ICD9/ICD10 codes, date of diagnosis, etc.)

VA Sleep clinic Patient Compliance Monitoring System Database

We will also access the Patient Compliance Monitoring System database used by the VA Sleep clinic to monitor patients' PAP use. This monitoring system is called EncoreAnywhere and is a HIPAA compliant system that has been approved nationally by the VA and is used clinically at all VA Medical Centers. The EncoreAnywhere database contains PAP usage data that has been transmitted via modem from Veterans' prescribed PAP devices. We will identify Veterans in this database with insufficient PAP use and merge this list with the CDW list to obtain contact information. Data abstracted from the EncoreAnywhere database will include:

- Unique patient identifiers (last 6 SSN)
- Name
- Date of birth
- Dates of PAP set-up, modem uploads
- Summary PAP usage data

CPRS electronic medical record

The data abstracted from CPRS will include:

- Dates of clinical sleep apnea testing (i.e., home or laboratory tests)
- Results of sleep apnea tests (i.e., AHI, RDI)
- Treatment prescribed (e.g., type of PAP, pressure settings)
- PAP usage data

Provider Referrals

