Participants in both groups will complete the Credibility/Expectancy Questionnaire (CEQ) after session 1 and session 5. This 6-item questionnaire measures whether subjects think (i.e., cognitively based credibility) and whether they feel (i.e., affectively based expectancy) treatment will help them improve. It will be used to assess for differences in credibility and/or expectancy between the intervention and control groups, to assess participant blinding. All sessions will be digitally recorded. and one of the co-investigators or the project psychologist will listen to the recordings to assess treatment fidelity.

Follow-up Data Collection

Participants will complete three follow-up assessments, including post-treatment (i.e., after session 5) and at 6 and 12 months follow-up. Each assessment will include a repeat of selected baseline questionnaires and a 7-day sleep diary.

In addition, objective cumulative PAP usage data will be accessed at each timepoint.

Post-treatment assessment (45 minutes)

Conducted one week after session 5 (in both groups) to assess initial effects of the intervention and control conditions. Participants will be given a 7-day sleep diary at the end of the session and will be instructed to complete it prior to the post-treatment visit. Research staff (blinded to group status and independent of the interventionists) will administer the following questionnaires:

- Generalized Anxiety Disorder-7
- Insomnia Severity Index
- Self-efficacy Measure for Sleep Apnea
- Behavioral Determinants of PAP Adherence questionnaire

- Pittsburgh Sleep Quality Index
- Epworth Sleepiness Scale
- Functional Outcomes of Sleep Questionnaire-10
- PROMIS-29 questionnaire

Six-month and 12-month follow-up assessments (45 minutes each)

These follow-up assessments will be conducted six months and 12-months from the date of randomization. These assessments will include the same questionnaires that were administered at the post-treatment assessment. Participants will also complete a 7-day sleep diary at each assessment timepoint.

Participant Payments

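### The primary t-test on PAP hours uses neither the randomization stratum nor recorded prior use, so its interval is wider than the stratified design warrants

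*Combined protocol and SAP*

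**What the plan says.** Under Data Analysis, Primary Aim 1, the outcome is mean nightly PAP hours over nights 1 to 180, counted "Beginning with the first night after randomization". An independent-groups t-test "was used to compare the average PAP usage between the treatment and control groups". No covariate or stratum term is named.

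The Randomization section stratifies on "any PAP use over the prior 12 months, versus" no use, in blocks of 4, on the ground that prior use may predict response.

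The section on the sleep clinic's compliance monitoring database lists "Summary PAP usage data" among the items abstracted, and the list for the medical record also includes PAP usage. Neither list mentions nightly hours or a time window. The statement under Follow-up Data Collection that "objective cumulative PAP usage data will be accessed at each timepoint" concerns the follow-up assessments and does not establish a pre-randomization record.

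The Aims 2 and 3 analysis does use baseline values, through group-by-time contrasts against baseline. The primary outcome is the only one analysed without any baseline information.

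**The concern.** The design treats prior use as prognostic enough to stratify on, and the analysis then drops it. Two things follow.

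- **Interval width.** Stratified blocking removes between-stratum imbalance, but an unadjusted t-test computes its standard error as if that had not happened. The reported interval is too wide whenever the stratum predicts later hours.
- **Prior hours among previous users.** The stratum is binary. A Veteran with one night of use eleven months ago and one now just short of the Medicare standard fall in the same stratum, although their expected later hours may differ. Blocking does not balance that difference and the t-test does not adjust for it.

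At stake is how precisely the trial states the size of benefit in hours per night. Adjustment estimates the same quantity, a difference in mean hours.

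**Working it through.** **Inputs from the documents.** The Sample Size table gives a detectable difference of "≥1.7 hours/night" with power 0.999 at n=90 and 0% attrition. On final size, "we continued enrollment until we achieved a sample of 106 randomized participants".

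**Assumptions.** Equal allocation (two arms, blocks of 4), two-sided 5% alpha, and a correlation ρ of 0.2 to 0.6 between prior and later hours. The documents give no SD, alpha or correlation. Two-sided 5% is the closer fit to the FOSQ row (d=0.64, stated power 0.806): it gives 0.826 with 84 analysed and 0.807 with 80, whereas one-sided gives about 0.90 with 84-85.

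**Step 1: the plan's power figure.** Without an SD, 0.999 cannot be reproduced independently, so I solved for the SD. With 45 per arm, noncentral-t power of 0.999 needs d = 1.077, so SD = 1.7/1.077 = 1.58 h. At 53 per arm the same SD gives power 0.9998.

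**Step 2: unadjusted interval at N=106.** SE = 1.58 × √(2/53) = 0.307 h. Half-width = 1.983 × 0.307 = 0.61 h.

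**Step 3: reported interval after adjusting for prior hours.** Multiply by √(1−ρ²).

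**Step 4: true sampling error under stratified blocking.** The t-test estimate already benefits from the stratification. Its true SE is about 0.307 × √(1−ρ²R²), where R² is the share of variance in prior hours explained by the stratum. For illustration, assume half are non-users and the others are uniform on 0.05-4 h (mean 2.025 h):

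- Variance within users = 3.95²/12 = 1.300, contributing 0.5 × 1.300 = 0.650.
- Variance between strata = 0.25 × 2.025² = 1.025.
- R² = 1.025/1.675 = 0.612.

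The true fall in SE is 1 − √(1−ρ²)/√(1−0.612ρ²).

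| ρ | Adjusted SE (h) | Reported half-width (h), from 0.61 | True fall in SE, this illustration | True fall in SE, simulation |
|---|---|---|---|---|
| 0.2 | 0.301 | 0.60 | 0.8% | 1-2% |
| 0.3 | 0.293 | 0.58 | 1.9% | 1-2% |
| 0.5 | 0.266 | 0.53 | 5.9% | 5-6% |
| 0.6 | 0.245 | 0.49 | 9.4% | 8-13% |

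The last column simulates the stratified design with blocks of 4 and N=106. A separate simulation with SD 1.6 h at ρ = 0.5 gave SEs of 0.286-0.290 for the t-test and 0.270-0.271 after adjustment, about 5-7%.

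**Step 5: the stratum term alone.** It leaves the sampling error of the estimate unchanged but brings the reported interval into line with it. At ρ = 0.5 the half-width is 0.61 × √(1−0.25×0.612) = 0.56 h (simulated 0.56-0.57). So at ρ = 0.5, 0.61 to 0.56 h corrects the reported interval, and 0.56 to 0.53 h is the real gain from prior hours.

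**Step 6: validity.** In simulation the t-test was unbiased. Its type I error was 0.041-0.052 at ρ = 0.2-0.3, 0.030-0.036 at 0.5 and about 0.024-0.031 at 0.6. It is nominal to conservative, not inflated.

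**Step 7: sensitivity to the SD.** The 1.58 h rests on one rounded power figure. If the SD were 3.0 h, power for 1.7 h at N=106 would be 0.824 unadjusted and 0.839, 0.916 or 0.951 at ρ = 0.2, 0.5 or 0.6.

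**The case against.** The strongest reply is that nothing here is invalid. The t-test is unbiased, chance imbalance is already inside its standard error, the coarse part of prior use is balanced by design, and power for 1.7 h is 0.999 on the plan's own row. All of that stands. A reader might infer a biased or underpowered primary test, and the documents support neither.

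Three further objections also stand:

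- **Data.** A reader might infer that pre-randomization nightly hours are in hand for everyone. The documents list only usage data, the clinic database holds only modem uploads, recruitment also runs through administrative data and provider referral, and some participants have no PAP device at entry. Stratum membership must be known for all 106; numeric hours are not shown to be.
- **Size.** It is tempting to say that adjustment makes 106 participants worth 141 at ρ = 0.5 (106/0.75). That compares adjustment with an unstratified design and so counts what blocking already delivers. Entry is also limited to insufficient users, which narrows the range of prior hours and may keep ρ low.
- **Timing.** The analysis section is in the past tense and already reports which covariance structures fitted best for Aims 2 and 3. Replacing the primary test after arm-level results are known would be a post hoc change.

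The objection does not remove the core point. The planned interval ignores a factor that the design was built on, and the stratum term needs no new data.

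**Conclusion.** The point holds as a cheap improvement in precision. The primary analysis omits both the stratum and prior use. Its reported 95% half-width of about 0.61 h would become 0.60 to 0.49 h for ρ from 0.2 to 0.6, while true sampling error would fall by about 1-2% at the low end, 5-6% at 0.5 and 8-13% at 0.6.

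These figures rest on the back-solved SD of 1.58 h, equal arms, two-sided 5% alpha, and assumed values for ρ and for the distribution of prior hours. At low ρ the gain is slight. Recovery of prior hours for all participants is unproven, so the firm part of the recommendation is the stratum term, with prior hours added where they exist.

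**What to change.** Fit a linear model of mean nightly PAP hours (nights 1-180) on arm, stratum and prior mean nightly hours, and report the adjusted mean difference with its 95% CI.

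- Take prior hours over one fixed pre-randomization window, written down before extraction.
- Set them to zero for the no-use stratum.
- For previous users whose hours were not recorded, use a missing indicator.
- If prior hours cannot be recovered for enough participants, adjust for the stratum alone. State in advance what counts as enough.

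If arm-level outcomes have not been seen, make this model primary and keep the t-test as support. If they have been seen, keep the t-test as primary and report the model beside it as a labelled sensitivity analysis. The SAP should state which case applies.

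The cost is a few lines of SAP text, one regression, and an extraction of prior hours that may be incomplete for devices without a modem. The stratum-only version needs no extraction.
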